5.2 EXCLUSION CRITERIA

An individual who meets any of the following criteria will be excluded from participation in this study:

- Lost more than 10 pounds in the last 6 months
- History of weight loss surgery
- Currently participating in another physical activity or weight loss program or research study that may interfere with participation in this study
- Currently meeting exercise recommendations of 150 minutes per week of moderate-to-vigorous physical activity
- Currently pregnant, pregnant within the past 6 months, or planning to become pregnant within the next 4 months
- Planning to relocate in the next 4 months
- Cannot attend weekly visits at the UNC Weight Research Program clinic
- Pre-existing medical condition(s) that preclude adherence to an unsupervised exercise program, as determined by items endorsed on the PAR-Q (Physical Activity Readiness Questionnaire)
- Treatment of diabetes with insulin or oral medications
- Report taking prescription or over the counter medication with a known impact on metabolism or weight
- Current treatment for cancer
- History of clinically diagnosed eating disorder
- Diagnosis of schizophrenia or bipolar disorder
- Hospitalization for a psychiatric diagnosis within the last year
- Report a past diagnosis of or current symptoms of alcohol or substance dependence
- Unwilling or unable to wear the CGM device continuously for the duration of the study
- On dialysis
- Have an implanted medical device such as a pacemaker

All participants will be required to obtain consent from their primary care provider in order to participate.

5.3 LIFESTYLE CONSIDERATIONS

During this study, participants are asked to:

- Refrain from using over-the-counter medications, dietary supplements, and prescribed medications for the purposes of weight loss; however, they will not be withdrawn if use is reported. Medication usage will be assessed at the pre-enrollment screening and change in medications, as well as adverse medical events, will be assessed at the 12-week study visit and documented in the Medical Events questionnaire.

5.4 SCREEN FAILURES

Screen failures are defined as participants who consent to participate in this study but are not subsequently assigned to the study intervention or entered in the study. An example of a screen failure would be a participant who comes for the baseline assessment and does not meet the eligibility criteria (such as a BMI or HbA1c that is out of eligible range).

If the participant does not meet inclusion criteria, staff will inform the individual that they do not meet criteria for this particular study and ask if they would be interested in being contacted about future studies.

5.5 STRATEGIES FOR RECRUITMENT AND RETENTION

Recruitment

Participants meeting diagnostic criteria for Type 2 diabetes (not treated by medication) and prediabetes will be recruited from the community through informational listservs, as well as through the UNC Health Care system using lists generated by the Carolina Data Warehouse.

If needed, we will use the UNC Informational listserv and boosted Facebook posts to advertise as well. Interested participants will be directed to a web page with study information. If they wish to determine their eligibility, they will complete an online REDCap screening questionnaire. Participants initially eligible on the web screen will be contacted by phone to complete screening.

All recruitment advertisements will encourage potential participants to visit a website with study information (purpose, eligibility criteria, time commitment, and incentives). The recruitment website will also have a link to a preliminary online screening questionnaire, which directs participants to a secure REDCap survey. Initial screening of basic eligibility and demographics will be done online, including questions on age, race/ethnicity, height, weight, basic health history, type 2 diabetes diagnosis, access to technology and availability to participate. If the individual is initially eligible, study

staff will contact the individual by phone for complete screening. Individuals who are ineligible will be notified via email.

All individuals who respond to our advertising will be eligible for enrollment independent of gender and race/ethnicity. As women are generally over-represented in weight control studies, we do not anticipate having inadequate representation by women. Also, given the diversity of the patient population in the UNC system and similar (if not higher) rates of overweight among minorities, access to participation will not be limited for these groups.

Enrollment

Once an individual has been deemed potentially eligible to participate, they will be invited to the clinic for an orientation to the study where study staff will provide further information about the study and allow the potential participants to ask questions. This procedure, whereby potential participants have a chance to determine if the study is a good fit for them, has been effective in our past studies for high rates of retention. If the individual decides to participate, they will provide informed consent for participation. They will have their height, weight, and HbA1c measured and complete questionnaires. After completion of the baseline assessments, the in-person individual sessions will begin.

COVID-19 Modifications:

Orientation sessions were delivered via Zoom after March 15, 2020. If the individual decides to participate, study staff will send an email link to the Informed Consent Form for the study participant to review and electronically sign in REDCap. Once the consent is signed, the online study questionnaires will be deployed to the participant. Once questionnaires are complete, the participant will be scheduled to attend the baseline assessment visit at the clinic and to attend the kickoff session.

Incentives

Participants will receive \$15 for completing the baseline assessment and \$25 for completing the 12-week assessment. Participants who complete the 12-week assessment will be allowed to keep the Fitbit and scale.

The small incentives are meant to offset the time for completing the study questionnaires, transportation costs for coming to clinic for assessments, and to ensure that we get adequate follow-up data once the study has been completed by the participant. The Fitbit and scale are relatively affordable devices that are widely available to the general public.

6 STUDY INTERVENTION

6.1 STUDY INTERVENTION(S) ADMINISTRATION

6.1.1 STUDY INTERVENTION DESCRIPTION

Intervention. The intervention is delivered through weekly in-person individual sessions and a mobile iPhone app that integrates diet, weight, and physical activity data to support self-regulatory behaviors. Additionally, participants use a Continuous Glucose Monitoring system to track and manage blood glucose. In the first weekly session, participants are oriented to the intervention and provided with their self-monitoring tools. They are encouraged to weigh and track PA, Red foods and BG daily and taught to use self-regulatory techniques for weight management and glycemic control. Similar to blood glucose self-regulation, participants are taught to compare the number on the scale each day to a standard or goal (weight loss goal) and, depending upon the comparison, make changes to their diet (i.e., Green foods or Red foods) or physical activity (i.e., moderate to vigorous physical activity (MVPA) or sedentary behavior (SB)) as needed. All participants are given an initial weight loss goal of 5%.

Dietary Intervention

Participants are guided to follow a Traffic Light Diet approach where foods are categorized into Green, Yellow, and Red categories. Users are encouraged to increase Green foods, moderate Yellow foods, and limit Red foods. Foods in the Green category include fruits, vegetables and certain very lean proteins. They are low in calories, fat, and sugar, and rich in nutrients. The high volume, water content and fiber in fruits and vegetables and the protein from the lean meats and egg whites in this category help promote satiety while consuming fewer calories. The Yellow category includes moderately lean proteins, legumes, low fat dairy, whole grains, starchy vegetables, and low fat dressings. These foods are higher in calories than green food but are still a good source of nutrients. Red foods are high in calories, fat, and/or sugar and are not a good source of nutrients. The goal in the Traffic Light Diet is to increase Green foods and to limit Red foods. This emphasis on increasing healthful eating has been hypothesized to reduce feelings of deprivation and hunger (37,38). In the Traffic Light approach followed in this study, users are allowed unlimited Green foods and are not given a specific target for Yellow food servings.

Each participant is given a personalized Red foods limit, which is determined by baseline weight. The intent of the goal is to result in a caloric reduction of 500-1000 per day. Participants are asked to monitor all of their foods for the first two weeks in order to orient them to the Traffic Light Diet system and to give them and their counselor a good idea of their overall intake pattern. After the first two weeks, they have the option to only monitor Red foods. During individual counseling sessions, interventionists have the option to set a goal for Green and/or Yellow foods and have the participant monitor those in the app, and/or to reduce the participant's Red Food limit if weight loss is not

progressing as desired. Lesson content encourages building healthy meals around green foods and participants are provided with meal plans and recipes that models this meal pattern.

Baseline Weight	Red Food Limit
< 200 lbs	3
200 - < 250 lbs	4
250+ lbs	5

Physical Activity Intervention

The physical activity goal for the study is to progress the participant to at least 150 minutes of moderate to vigorous physical activity per week. An initial goal is based on baseline levels of PA as reported by the participant. Progression will occur each week based on individual progress of the participant.

Baseline Weekly

MVPA	Active Minutes Goal
< 50	10 min/day
50-75	15 min/day
76-100	20 min/day
101-125	25 min/day
126-149	30 min/day
Maximum	60 min/day

PA GOAL PROGRESSION

When total active minutes for the week is equal to or above [AM Goal*5], then increase daily goal for the next week by 5 minutes

Otherwise, active minutes daily goal remains the same the next week

Example, if goal is 15 min/day, the 5-day equivalent would be 75. If participant gets 80 min, then daily goal increases by 5, to 20 min/day. But if participant only got 60 min, then their daily goal for the new week would stay at 15 min/day

Intervention app

During the first individual session, the interventionist will work with the participant to download the app onto the participant's smartphone, familiarize them with the app, and set personal goals for weight, diet and physical activity, and BG monitoring.

- Weight Goal and Monitoring: Participants will be provided a Withings Wi-Fi Smart Scale digital scale and instructed on setup and procedures for daily weighing.
- Dietary Goal and Monitoring: Interventionists instruct on the Red foods list and monitoring of Red foods in the app. They will be instructed on portion size estimation and self-monitoring best practices (timing proximal to consumption). During the first week, participants will be advised to monitor all of their foods and work towards meeting their daily Red food goal.
- Physical Activity Goal and Monitoring: Participants will be provided with a Fitbit Inspire and will set up the device and the app to allow for data transfer. They will receive a weekly physical

activity goal based on baseline physical activity reported on the online screener. Participants will also be advised on using the Fitbit to monitor sedentary time and to target sedentary behavior throughout the day.

- **BG Goals and Monitoring:** Participants will be provided with an Abbott Freestyle Libre device, which is a Continuous Glucose Monitoring (CGM) unit. Recent advances in technology have made CGM much less invasive and simplified, thereby allowing for a better picture of glucose control given the number of data points available without the burden that previous CGM units presented. The interventionist will work with the participant to set goals for monitoring and ensure comprehension of CGM procedures. Study participants will be instructed on placement of the CGM sensor on the back of the arm. The sensor is worn for 14 days continuously, and then replaced. The participant will scan the sensor using a handheld device or iPhone at different points throughout the day (upon waking, before meals, 1 ½ - 2 hours after meals, but no less than every 8 hours) and to “mark” eating and activity events in the scanning device or iPhone app. The data will be uploaded to the Freestyle Libre system. The study interventionist will have access to the data through a web-based portal and will review this information with the participant at weekly coaching sessions. Participants will be taught to interpret their blood glucose information and to use it to inform diet and physical activity behaviors.
- **Feedback:** The app provides graphical feedback comparing goals to behaviors and a weekly feedback message from the counselor that encourages adherence to the goals of daily weighing, monitoring and meeting Red foods and physical activity goals. For the purposes of this study, more rigorous intervention feedback will be delivered by the interventionist at weekly sessions.

Behavioral Lessons

A standard behavioral intervention based on the DPP (used by [name] effectively in both face to face and Internet formats) will be adapted for this protocol. Behavioral weight control approaches are founded on teaching skills and providing the support necessary to enable participants to adhere to the diet and physical activity prescription in their intervention. For the dietary intervention, materials will be adapted to reflect the Traffic Light Diet focus and modules for decreasing sedentary behavior will be added to those for increasing MVPA. Materials will be adapted with a focus on T2D. Additional materials and activities will be added specifically on self-regulation of weight and BG in relation to diet and physical activity behaviors. Lessons will be presented within the app. Brief review of the content will be done during individual sessions to assess comprehension and to explore personal applications.

Coaching Support

Individual counseling sessions will be semi-structured and led by Master’s level or higher interventionists trained in behavioral weight control. Sessions will occur weekly (12 sessions) and typically last 30-45 minutes. For the first 4 weeks of the study, all sessions will be conducted at the UNC Weight Research Program clinic. Participants will be encouraged to attend in-person sessions for the duration of the study, however they will be given the option to complete the remaining 8 sessions through phone or video chat (Zoom) if desired. (Note: the remote mode of delivery became the primary delivery mode due to COVID-19 restrictions.)

6.1.2 DOSING AND ADMINISTRATION

Described in section above 6.1.1

6.2 FIDELITY

6.2.1 INTERVENTIONIST TRAINING AND TRACKING

To ensure intervention fidelity, study meetings will be held weekly. At these meetings, the research team will discuss issues relevant to study progress, including enrollment, participant safety (adverse events), participant retention, and protocol compliance. Summaries of the team meeting minutes will be available for inspection when requested by any of the regulatory bodies charged with the safety of human subjects and the integrity of data including, but not limited to, the oversight of the Office of Human Research Ethics (OHRE) Biomedical IRB, or the North Carolina TraCS Institute Data Safety Monitoring Board (DSMB).

6.3 MEASURES TO MINIMIZE BIAS: RANDOMIZATION AND BLINDING

This is a single arm study. Therefore, randomization is not applicable.

Due to the size of this pilot study and staffing limitations during the COVID-19 pandemic, study staff will not be blinded for the assessments. Assessment staff will be trained and strictly adhere to assessment protocol.

6.4 STUDY INTERVENTION COMPLIANCE

Interventionists will review food, weight, and activity progress through an administrative web portal prior to individual sessions. During the weekly session, the interventionist will review self-monitoring records with the participant, set weekly goals, review behavioral lesson content introduced in the app, facilitate problem solving of any barriers the participant is having, and adapt treatment recommendations based on the needs of the participant.

6.5 CONCOMITANT THERAPY

For this protocol, participants will be discouraged from using over-the-counter medications and dietary supplements, and prescribed medications for the purposes of weight loss; however, they will not be withdrawn if use is reported. Medication usage will be assessed at the pre-enrollment screening and change in medications, as well as adverse medical events, will be assessed at the 12-week study visit and documented in the Medical Events questionnaire.

6.5.1 RESCUE MEDICINE

N/A

7 STUDY INTERVENTION DISCONTINUATION AND PARTICIPANT DISCONTINUATION/WITHDRAWAL

7.1 DISCONTINUATION OF STUDY INTERVENTION

Discontinuation of the study intervention without withdrawal from the study will only occur at the request of the participant if they are no longer willing or able to adhere to the study intervention for personal (not medical or safety) reasons. When a subject discontinues from the study intervention but not from the study, final assessment measures will be completed as indicated by the study protocol

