Minimization of risks: To ensure medical readiness to begin physical activity, participants will complete a physical activity readiness questionnaire (PAR-Q). The PAR-Q assesses for the following medical conditions: heart problems, chest pains, faintness or dizzy spells, high blood pressure, bone, or joint problems such as arthritis that has been or could be aggravated by exercise, prescription medication use, and other medical reasons why exercise would not be advisable. Participants endorsing yes to any items on the PAR-Q (experience of heart problems, frequent chest pains, faintness or dizziness, bone or joint problems, on prescription medications for blood pressure or a heart condition) will be excluded from the study.

We also will monitor any major musculoskeletal problems that develop during the intervention (e.g., broken bones) using a medical events questionnaire at 3 months and determine whether these appear related to our study. Participants who develop musculoskeletal problems or other health problems that may affect safe participation will be instructed to stop exercising until the problem resolves and their physician approves resumption of physical activity.

Participation is fully voluntary, and we will ask participants to report any problems to the study researchers.

2. Risk of wearable devices: There is also the possibility of minor skin irritation associated with wearable devices.

Minimization of risk: We will recommend taking the device off occasionally, not wearing it too tightly, and keeping it clean and dry. If participants experience skin irritation, we will suggest that they contact a member of the study team to discuss the issue and determine whether they would like to continue participating in the study.

3. Risk of using a phone while driving: It is dangerous to pay attention to a cellular phone while driving, walking, or doing any activity that requires attention.

Minimization of risk: We will strongly recommend that participants exercise good judgment on this while participating in this study and will ask that they not open the application or view any notifications or messages while they are driving.

4. Risk of CGM: There is a small risk that the adhesive used to attach the sensor to the arm will cause skin irritation.

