Minimization of risk: Through instructions on usage of the CGM will be provided to the participant at the beginning of the study. Proper placement and care will be emphasized and, if irritation does occur, participants will be instructed to discontinue use of the sensor and alert the study staff.

5. Risk of finger stick: Approximately 3 drops of blood will be removed by finger stick. This is a standard method used to obtain blood for routine hospital laboratory tests. The participant may experience pain when the lancet goes into their finger. Other than this momentary pain, the discomfort of finger stick should be minimal. However, in about 10% of the cases a small amount of bleeding under the skin will produce a bruise (hematoma). A small scar may persist for several weeks. The risk of local infection is less than 1 in 1,000.

Minimization of risk: Staff are trained in the sanitary collection of blood using gloves, prepping the area with an alcohol swab, having the participant apply pressure to the finger after the finger stick and application of a bandage if needed.

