7.2 PARTICIPANT DISCONTINUATION/WITHDRAWAL FROM THE STUDY

Participants are free to withdraw from participation in the study at any time upon request. Participants will be withdrawn from the study should they experience greater than minimal risk as described in section 2.3.

In addition, an investigator may discontinue a participant from the study for the following reasons:

- Significant study intervention non-compliance, unless varying compliance is an aspect of the study objectives
- Lost-to-follow up; unable to contact subject (see **Section 7.3, Lost to Follow-Up**)
- Participants who become pregnant during the study, as weight loss is contraindicated.
- Any event or medical condition or situation occurs such that continued collection of follow-up study data would not be in the best interest of the participant or might require an additional treatment that would confound the interpretation of the study
- The participant meets an exclusion criterion (either newly developed or not previously recognized) that precludes further study participation

The reason for participant discontinuation or withdrawal from the study will be recorded on the Case Report Form (CRF). Subjects who sign the informed consent form and are randomized but do not receive the study intervention may be replaced. Subjects who sign the informed consent form, and are randomized and receive the study intervention, and subsequently withdraw, or are discontinued from the study, will not be replaced.

The research team will provide continuous monitoring of participant safety and periodic reporting to the UNC IRB as required, including any Unanticipated Problems/Severe Adverse Events that may have occurred during the study. Data safety and monitoring activities continue until all participants have completed trials and until all participants have been followed to the point at which study-related adverse events would likely no longer be encountered.

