8.2 SAFETY AND OTHER ASSESSMENTS

Safety management in this study is intended to achieve 4 objectives: 1) to minimize the occurrence of adverse effects; 2) to effectively manage adverse events as they relate to the study; 3) to identify when the intervention should be suspended because of concerns for participant safety; and 4) to determine when the intervention may be resumed after having been suspended.

Should any concerns arise during data collection, they will be addressed immediately by study personnel and the PI will be notified as soon as possible. Though unlikely, should any concerns arise after data

collection, subjects will be given the study coordinator's contact information to share their concerns and the PI will address concerns directly or through appropriate referrals. Any concerns that arise over the course of the study will be recorded and aggregated as part of the feasibility data and shared with the research team and the IRB as necessary.

We do not anticipate that any questions, anthropometric measurements, observations will cause discomfort or embarrassment, but participants may stop or refuse collection of data at any time. Participants will be informed of potential safety risks in the informed consent.

The research team will provide continuous monitoring of participant safety and periodic reporting to the UNC IRB as required, including any Unanticipated Problems/Severe Adverse Events that may have occurred during the study. Data safety and monitoring activities continue until all participants have completed trials and until all participants have been followed to the point at which study-related adverse events would likely no longer be encountered.

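### Sections 7.1 and 7.2 provide no 12-week outcome collection after a medical or safety withdrawal, so those participants drop out of the primary weight result and the CGM ratings

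*Combined protocol and SAP*

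**What the plan says.** Section 7.1 sets the only route for leaving the intervention while staying in the study: "Discontinuation of the study intervention without withdrawal from the study will only occur at the request of the participant", and then only where the person is "no longer willing or able to adhere to the study intervention for personal (not medical or safety) reasons". Final measures are tied to that route: "When a subject discontinues from the study intervention but not from the study, final assessment measures will be completed as indicated by the study protocol".

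Section 7.2 deals with safety by ending study participation: "Participants will be withdrawn from the study should they experience greater than minimal risk as described in section 2.3". Section 2.3 describes individual risks and how to reduce them, but sets no such level. Section 7.2 also lists reasons for which the investigator may discontinue someone. They include a medical event after which further data collection would not serve the participant, and an exclusion criterion that is newly met and rules out continuing. Section 8.3.9 withdraws participants who become pregnant.

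Other sections describe medical or safety stops without mentioning withdrawal:

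- Under 2.3.1, participants with a musculoskeletal or other health problem "will be instructed to stop exercising until the problem resolves and their physician approves resumption of physical activity".
- Under 2.3.1, if the CGM adhesive irritates the skin, "participants will be instructed to discontinue use of the sensor and alert the study staff".
- The safety objectives in 8.2 include "to determine when the intervention may be resumed after having been suspended".

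Section 5.2 excludes anyone "Unwilling or unable to wear the CGM device continuously for the duration of the study".

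**The concern.** Whether the endpoint is observed depends on why the person stopped. Someone who loses interest is still asked for a 12-week weight. Someone withdrawn because the intervention was unsafe for them is not. The second group is the more informative one for a feasibility study: people who could not exercise safely or could not tolerate the sensor probably did less well on weight and would probably rate the CGM less favourably.

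Weight change is the primary endpoint. CGM satisfaction and acceptance are exploratory endpoints that bear directly on the feasibility aim. Section 9.4.1 intends the estimates of change to feed effect sizes for an R01 application, so optimism here would carry into the planning of the larger trial.

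**Working it through.** **Inputs from the documents.** N = 20 (Synopsis). Weight change is measured from baseline to 12 weeks (Synopsis, Section 3). The CGM surveys are read at 12 weeks (Section 3). Weight and HbA1c are analysed by paired t-test with no missing-data rule (9.4.1). The population is intention-to-treat, worded as all randomized participants (9.3) in a study without randomization (6.3), so the natural reading is everyone enrolled. Participants who leave after receiving the intervention are not replaced (7.2). Section 9.2 says the sample size was not derived statistically, and the plan gives no SD, effect size or dropout rate. There is therefore no planned figure to reproduce, and everything numerical below is illustration.

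**Step 1: the passages side by side.**

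| Situation | Section | Stays in study? | 12-week measures provided for? |
|---|---|---|---|
| Stops for personal reasons, at own request | 7.1 | Yes | Yes |
| Risk above minimal (undefined) | 7.2 | No | None described |
| Pregnancy | 8.3.9 | No | None described |
| Health problem, exercise paused | 2.3.1 | Implied yes | Not addressed |
| Sensor irritation, sensor removed | 2.3.1 | Not stated; see 5.2 with 7.2 | Not addressed |
| Intervention suspended, then resumed | 8.2 | Implied yes | Not addressed; no matching route in 7.1 |

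A paired t-test needs both weights, so rows two and three leave the analysis.

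**Step 2: effect on mean weight loss.** Assume k of 20 are lost and would have had zero change. If the remaining 20 − k have mean loss m, the mean for all 20 is m(20 − k)/20. The overstatement is 20/(20 − k) − 1 = k/(20 − k):

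- k = 1: 1/19 = 5.3%
- k = 2: 2/18 = 11.1%
- k = 3: 3/17 = 17.6%

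More generally, if those lost differ from those remaining by d percentage points of weight change, the mean shifts by (k/20)·d. For k = 1 to 4 that is 0.10 to 0.40 points with d = 2 (assumed). It is 0.23 to 0.92 points with d = 4.6, the gap between more and less frequent weighers in the breast cancer survivor pilot in Section 2.2 (−4.9% against −0.3%), used only as a scale.

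**Step 3: precision.** The 95% half-width is t(0.975, n − 1)·SD/√n. With the SDs of that pilot (2.6 and 6.3 points, borrowed), going from n = 20 to n = 17 moves it from 1.22 to 1.34, or from 2.95 to 3.24. Little precision is lost; the issue is bias.

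**Step 4: CGM ratings.** If x of the other 19 accept the device and the one lost person would not have, the percentage moves from x/20 to x/19, a change of x/380. That is 5.0 points at x = 19, 2.6 at x = 10 and 1.3 at x = 5. Five points is the ceiling. Section 3 specifies survey responses, not a percentage, so this applies only if one is reported.

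**Step 5: chance that it arises.** With an assumed medical-withdrawal risk p per person, the chance of at least one among 20 is 1 − (1 − p)^20: 33%, 64%, 88% and 96% for p = 2%, 5%, 10% and 15%.

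**The case against.** The strongest reply is that the documents are less severe than Section 7 read alone, and much of it stands.

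- **Harm follow-up.** A reader might infer that withdrawn participants take their harm data with them. The documents do not support that. Section 8.3.4 records non-serious events for 7 days and serious events for 30 days after participation ends, and follows events until they resolve or stabilise. Sections 7.2, 8.2 and 8.3.5 continue safety monitoring. What is missed is the 12-week Medical Events form, which 2.3.3 describes as a catch for events not raised in coaching.
- **Everyone stopped for a medical reason must leave.** This too is tempting, but too broad. Section 2.3.1 allows an exercise pause and sensor removal without stating withdrawal, and exercise is one component among several. The 8.2 wording on suspension is a general objective and could be read at study level.
- **Sensor irritation forces withdrawal.** Being unable to wear the CGM is an exclusion in 5.2, but the 7.2 clause on newly met exclusions is discretionary and limited to criteria that rule out further participation. The sections leave the outcome unclear; they do not dictate it.
- **Silence is not prohibition.** No passage forbids a 12-week visit after withdrawal. That is true, but 7.1 states a restriction and attaches final measures to that route alone, so staff following the text have no basis for recalling a withdrawn participant.
- **Small pilot.** There is no hypothesis and no powered test, and the problem arises only if someone is actually withdrawn. CGM data uploaded before withdrawal still count towards adherence. This limits the weight of the point without removing it.

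**Conclusion.** The concern holds in a limited form. Sections 7.1 and 7.2 together provide no 12-week weight, HbA1c, CGM survey or Medical Events form for participants withdrawn for medical or safety reasons, and the trigger for mandatory withdrawal is undefined. This conflicts with the population in 9.3, and the paired t-test does nothing to repair it.

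The overstatement of mean weight loss is 5%, 11% or 18% for one, two or three such losses if those lost would have had no change. It would be zero if they had done as well as the rest, and reversed if they had lost more, so the direction is likely but not certain. The number lost is an assumption; the documents give no rate. The effect on any CGM acceptability percentage is at most 5 points per person lost. The matter deserves correction because the repair is cheap and the estimates are meant for planning a larger trial.

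**What to change.** - Reconcile 7.1 and 7.2 with the exercise pause and sensor removal in 2.3.1, the suspension and resumption in 8.2, and the CGM-wear exclusion in 5.2. Say what 7.2 means by its reference to Section 2.3. Which clinical stopping rule governs is for the investigator to settle.
- Separate stopping the intervention from stopping data collection. Ask participants who stop all or part of the intervention for any reason, medical and safety reasons included, to complete the existing 12-week weight, HbA1c, questionnaires and Medical Events form. The exceptions are withdrawn consent and the case in 7.2 where further data collection is not in the participant's best interest.
- State how pregnancy withdrawals under 8.3.9 are handled in the weight analysis, so that weights taken during pregnancy do not enter it by default.

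The cost is a minor amendment to the wording, since the 12-week visit already exists. The downside is that a few off-intervention weights enter the primary analysis and make the mean loss slightly less favourable.
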